6.0 Study Intervention

The study intervention for Cohort 1 is delivery of HIV medication at Project Trust, rather than in the BMC HIV Clinic. Project Trust (PT) is a street-based drop-in clinic that is focused on STD testing, treatment, harm reduction, and social services engagement. PT engages in outreach work, provides individuals with substance use disorder safe injection kits, and is a well-established community site for the target population frequenting the area, which is home to a high number of individuals who are homeless, diagnosed with substance use disorder, and are living with HIV. Study staff who will be administering the injection are all trained clinicians (either nurse practitioners or physicians) and are BMC staff. Individuals administering the injection will all be listed on the BUMC Internal Review Board study protocol.

There is not a clinical intervention or any intervention beyond data collection for Cohorts 2 or Cohort 3. Cohort 2 will be receiving their CAB-RPV LA within the BMC HIV clinic as their standard care. Cohort 3 will be receiving standard of care (not CAB-RPV LA) and will be patients of the BMC HIV clinic. Individuals enrolled in all three cohorts will be asked to complete a survey at study enrollment (baseline), between 2-4 months after their enrollment (midpoint) and a final follow up between 6 - 8 months post baseline. Clinical data will be obtained from the BMC EHR via the clinical data warehouse at these time periods and no other data will be collected directly from study participants for Objective 2.

7.0 Study Procedures

Medication regimen

	Cohort 1	Cohort 2
Month 1	Optional Oral lead-in (up to 28 days) 30 mg tablet of Vocabria 25 mg tablet of Edurant Opt out of Oral Lead-In:	(Anticipated) Maintenance Dose

Protocol Title: **CAB-RPV LA Implementation Strategies for High-Risk Populations**

	Initiation Injection (600 mg of cabotegravir and 900 mg of Rilpivirine)	
Month 2	
Oral Lead-in Completed: Initiation dose (600 mg of cabotegravir and 900 mg of rilpivirine)
 
Oral Lead-in not done: Maintenance Dose (400 mg of cabotegravir and 600 mg of rilpivirine)
	Monthly: Maintenance Dose Bi-monthly: No Injection
Month 3	
Oral Lead In completed: Maintenance Dose (400 mg of cabotegravir and 600 mg of rilpivirine)
 
Oral Lead In Not Done: Monthly: Maintenance Dose Bi-Monthly: No Injection
	Monthly: Maintenance Dose Bi-Monthly: Maintenance Dose
Month 4	
Oral Lead In: Monthly: Maintenance Dose Bi-Monthly: No Injection
 
No Oral Lead In: Monthly: Maintenance Dose Bi-Monthly: Injection
	Monthly: Maintenance Dose Bi-monthly: No Injection
Month 5	
Oral Lead In: Monthly: Maintenance Dose Bi-Monthly: Maintenance Dose
 
No Oral Lead In: Monthly: Maintenance Dose Bi-Monthly: No Injection
	Monthly: Maintenance Dose Bi-Monthly: Injection
Month 6	
Oral Lead-In: Monthly: Maintenance Dose Bi-Monthly: No Injection
 
No Oral-Lead In: Monthly: Maintenance Dose Bi-Monthly: Injection
	Monthly: Maintenance Dose Bi-monthly: No Injection
Month 7	
Oral Lead In: Monthly: Maintenance Dose Bi-Monthly: Injection
 
No Oral Lead In:
	Monthly: Maintenance Dose Bi-Monthly: Injection

	Monthly: Maintenance Dose Bi-Monthly: No Injection	
--	---------------------------------------------------------------------	--

7.1 Cohort 1 Recruitment, Screening & Enrollment

Cohort 1 Recruitment and Screening:

Project Trust Recruitment: When an individual who appears to meet the inclusion criteria for Cohort 1 presents at PT, the ARCH outreach worker or PT staff will inquire about their interest in participating in the study. For those who are interested, PT staff will make a warm handoff to study staff.

Faster Paths Recruitment: Faster Paths is a substance use urgent care clinic at BMC that helps patients access substance use treatment as well as HIV testing and care. When an individual who meets study criteria presents to Faster Paths, the Faster Paths clinicians will inquire about potential interest in study participation. If the individual indicates they are interest, the Faster Paths staff will make a warm handoff to study staff.

Boston Living Center: The Boston Living Center is a program located in the Back Bay that serves people living with HIV. In order to utilize Boston Living Center programs, individuals must present both a diagnosis letter as well as a referral letter. Study staff will set up a table during their lunch service, which all Boston Living Center members are eligible to participate in, and have a study flyer that details the study information and inclusion criteria. If individuals indicate that they are interested in participation, study staff will have conduct the screening consent with them utilizing the Screening Consent Form (Appendix A) as well as have the potential participant sign a Release of Information if they indicate they are not a current BMC patient.

It will be necessary to confirm that all potential participants are eligible for the study. To make this determination, study staff will consent the potential participant to access their Electronic Health Records using the Screening Consent Form (Appendix A).

- If a potential participant indicates that they are not a current BMC patient and receives their care elsewhere, study staff will request that the potential participant sign a Release of Information so that a study clinician may contact their current provider to obtain documentation of their care history in order to complete the eligibility screening, as well as discuss with their current provider whether the potential participant is a good candidate for the monthly or bi-monthly injection.
- If a potential participant is a BMC patient, study staff will obtain consent to move forward with the participant's care team in order to determine that the potential participant is eligible for the study.

All decisions will be made by study clinicians who will review medical documentation to determine that the potential participant meets eligibility criteria. Participants must be virally suppressed prior to enrollment, meaning that their HIV-1 ribonucleic acid measures less than 50 copies per mL. If a potential participant's EHR review indicates that they have a history of integrase inhibitor RT mutations suggesting resistance to Cabotegravir or Cabenuva, have demonstrated they have resistance to either an INSTI or an NNRTI, that the potential participant is currently pregnant, breastfeeding, or that the potential participant has HIV 1 with an HIV 2 co-infection or an HIV 2 infection, they will be deemed to be ineligible. Individuals who are not HIV positive, individuals under the age of 18 and individuals who do not speak English or Spanish are also ineligible. Individuals who are not virally suppressed are ineligible. Individuals who are not willing

Protocol Title: **CAB-RPV LA Implementation Strategies for High-Risk Populations**

to take CAB-RPV LA after detailed discussion of what the use of CAB-RPV LA will entail, or are unable to undergo clinical testing to confirm eligibility will be excluded. Individuals who are on drugs that have known interactions with Cabenuva, including but not limited to carbamazepine, oxcarbazepine, phenobarbital, phenytoin, St Johns Wort, systemic Dexamethasone, rifabutin, rifampin and rifapentine. Individuals who have chronic Hepatitis B infection will also be excluded. All women with child-bearing potential will have a pregnancy test conducted at a CLIA approved lab to rule out pregnancy.

Study staff will contact every individual who was screened within two weeks of screening (once test results are received and study clinician has confirmed whether or not they are eligible) and let them know if they are eligible for enrollment. Study staff will ask eligible individuals to return to PT for final study enrollment. If the potential participant is ineligible for enrollment due to being unsuppressed, study staff will encourage the potential participant to re-engage in their care in order to achieve suppression, and reach out to study staff once their viral load is undetectable for enrollment. If potential participants are ineligible for enrollment based on other criteria, study staff will refer back to clinical staff from PT to make an appropriate referral.

Once an individual in Cohort 1 is determined eligible and agrees to participate, they will meet with study staff at PT to complete the consent form to enroll in the study. Study enrollment will involve the following procedures:

- Study staff will contact the participant within 2 weeks of initial screening if participant is eligible for participation to schedule a meeting date for full consent procedures, and to collect baseline questionnaire data, as described above. Study staff will log this contact in the study log book (Appendix H).
- Prior to the consent and initial survey meeting, study staff will create a folder that contains a copy of the participant's screening consent form (Appendix A), a blank enrollment consent form (Appendix B), a blank Electronic Health Record Review Form (Appendix E), a blank Participant Questionnaire (Appendix F), and a blank Locator form (Appendix G). This folder will be labeled with their individual Study ID. The study ID key will be the following: Study ID Key: O2XXX – XXX is the equivalent of the number patient that they are. For example, the first person to be consented and enrolled into the study will be Participant Number O2001. The project manager will assign this number when participants are enrolled. This key will be used for participants in all three cohorts.
- Participants will have the consent form read to them and be asked to sign the consent form. These consent forms will be stored separately from data collection forms and will be kept in a locked filing cabinet. Study staff will be the only individuals who have access to this cabinet. The participant will have opportunities throughout the consent process to ask questions to both study staff and study clinician. After all questions are addressed to the participant's satisfaction, the baseline questionnaire will be completed.

Cohort 1 study intervention

All activities will be done on label. Therefore, before beginning CAB-RPV LA, participants who are meet the clinical criteria will discuss transitioning to the CAB+RPV oral RPV lead in if the participant and clinician choose to. The CAB-RPV LA oral lead-in is optional, which is FDA approved and on label. If the participant and their provider choose to begin the CAB+RPV oral lead-in, the procedure will take place as follows:

- Participants may be initiated onto a maximum 4 week CAB+RPV oral lead-in to monitor for side effects. The oral lead-in is comprised of one 30 mg tablet of Vocabria, and one 25 mg tablet of Edurant. Initial lab draws will include Genotype, HIV Viral Load, T Cell Subset, Comprehensive Metabolic Profile (which includes LFTs). Labs can be drawn at either the Shapiro Phlebotomy Lab,

Protocol Title: **CAB-RPV LA Implementation Strategies for High-Risk Populations**

or directly at Project Trust. If labs are drawn at Project Trust, PT staff will bring all lab tubes to Shapiro lab following standard Project Trust procedure. If participants choose to take the oral lead-in, they will be asked to complete the full 28 day course. If participants choose to take the oral lead-in, they will also be asked to check in with Project Trust staff weekly to monitor for adherence and assess any potential adverse events.

- Study staff will confirm with participant the date of their first injection. This contact will be recorded in the study Log Book (Appendix H). Study staff will confirm with clinician at PT the time and date of injection.

If the participant chose's to not take the oral lead-in mediation, the participant will proceed directly to the initiation injection once they have completed all required lab work, including HIV labs confirming that they are virally suppressed (> 50 copies per mL), and a comprehensive metabolic panel. The participant and their clinician will determine a date for the initiation injection. As the medication will need to be obtained from the pharmacy, participants will not be able to receive their initiation injection on the same day as they are enrolled into the study.

- At the time of the injection, during the 15 minute waiting period, study staff will sit with the participant and remind them of the target date for the next injection. This date will be recorded in the study Log Book. The month following the initiation dose, participants receive a maintenance dose. Once the participant has received the maintenance dose, the participant and their clinician may discuss whether the participant would like to shift to receiving the injection every other month rather than every month. The clinician and the participant may choose whether to receive the injection every month, or every other month per CID standard of care and the medication package insert.
- One week prior to each scheduled injection date, study staff will contact participant via their preferred contact method determined on the Locator Form to confirm injection date and confirm with the community-based clinician administering the injection.
- One day prior to injection date, study staff will contact participant for reminder.

Below is a table that outlines when all evaluation activities occur:

Month	Cohort 1	Cohort 2	Cohort 3
1	
• Screening• Enrollment• Comprehensive Metabolic Panel• Baseline Data Collection• Participant may choose to take 28 days of Oral Lead-In medication• If participant opts out of the oral lead-in, they will receive their Initiation Injection during this time point	
• Screening• Enrollment• Baseline Data Collection	
• Screening• Enrollment• Baseline Data Collection
2	
• Oral lead-in: Initial Injection• No Oral Lead-In: Maintenance Dose		

Protocol Title: **CAB-RPV LA Implementation Strategies for High-Risk Populations**

3	
 • Potential Midpoint Data Collection • Oral Lead-in: Maintenance Dose • No Oral Lead-in: Monthly: Injection, Bi-Monthly: No Injection 	
 • Potential Midpoint Data collection 	
 • Potential midpoint data collection
4	
 • Potential Midpoint Data Collection • Oral Lead-In: Bi-Monthly: No Injection, Monthly: Injection • No Oral Lead-In: Monthly: Maintenance Dose, Bi-Monthly: Injection • Comprehensive Metabolic Panel 	
 • Potential Midpoint Data Collection 	
 • Potential midpoint data collection
5	
 • Potential Midpoint Data Collection • Oral-Lead In: Monthly: Maintenance Dose, bi-Monthly: Injection • No Oral Lead-In: Bi-Monthly: No Injection, Monthly: Injection 	
 • Potential Midpoint Data Collection 	
 • Potential midpoint data collection
6	
 • Oral Lead-In: Bi-Monthly: No Injection, Monthly: Injection • No Oral Lead-In: Bi-Monthly: Maintenance Dose, Monthly: Injection 		
7	
 • Oral Lead-In: Bi-Monthly: Maintenance Dose, Monthly: Injection • No Oral Lead-In: Bi-Monthly: No Injection, Monthly: Injection • Potential endpoint Data Collection 	
 • Potential Endpoint Data collection 	
 • Potential endpoint data collection
8	
 • Potential endpoint Data Collection 	
 • Potential Endpoint Data Collection 	
 • Potential Endpoint data collection
9	
 • Potential Endpoint data collection 	
 • Potential endpoint data collection 	
 • Potential endpoint data collection

Protocol Title: **CAB-RPV LA Implementation Strategies for High-Risk Populations**

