5.0 Study Subject Selection

5.1 Subject Inclusion Criteria

Cohort 1: Age \geq 18 years, English or Spanish speaking, HIV-positive, labs indicate that they are a candidate for the medication and virally suppressed, meaning that their HIV-1 ribonucleic acid is less than 50 copies per mL. Individuals enrolled in Cohort 1 must be willing to complete the locator form (Appendix G) in order to receive appointment reminders prior to their monthly/bi-monthly injection and ongoing follow-up by outreach and study staff to maximize potential for adherence.

Cohort 2: Currently enrolled in care at CID and receiving CAB-RPV LA injection, age \geq 18 years, English or Spanish speaking. Individuals enrolled must be willing to complete the locator form in order to receive appointment reminders prior to follow-up data collection.

Cohort 3: Enrolled in care at CID but not receiving CAB-RPV LA, age \geq 18 years, matched to participants demographically and in terms of other characteristics in Cohort 1 at a 1:1 ratio. Individuals in Cohort 3 will be receiving the Standard Care for HIV treatment in CID. Standard of care for this group includes access to regular appointments with their HIV provider, oral ART, case management services, etc. Individuals enrolled must be willing to complete the locator form in order to receive appointment reminders prior to follow-up data collection.

Our goal for all three cohorts is to enroll a percentage of women that is equivalent to the number of female patients served by the sites, approximately 20-30% female. Similarly, we will ensure that our sample includes individuals of color proportional to their representation within the setting across all three cohorts.

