5.2 Subject Exclusion Criteria

Individuals who are not HIV positive, individuals under the age of 18 and individuals who do not speak English or Spanish will be excluded. Individuals who are not virally suppressed prior to beginning CAB will be excluded (excluding Cohort 3). Individuals who are not willing to take CAB-RPV LA after detailed discussion of what the use of CAB-RPV LA will entail, or are unable to undergo clinical eligibility testing to confirm eligibility will be excluded (excluding Cohort 3). If they have a history of integrase inhibitor mutations suggesting resistance to Cabotegravir or Cabenuva, a history or evidence of resistance to either INSTI or NNRTI, are currently pregnant or breastfeeding, or have HIV 1 with an HIV 2 co-infection or an HIV 2 infection, they will also be excluded. Individuals who have hepatic impairment at baseline lab draws will be excluded. Individuals who are on drugs that have known interactions with Cabenuva (including but not limited to carbamazepine, oxcarbazepine, phenobarbital, phenytoin, St Johns Wort, systemic Dexamethasone, rifabutin, rifampin and rifapentine) will be excluded. Individuals who have chronic Hepatitis B infection will also be excluded. If an individual is receiving CAB-RPV LA at CID, they are not eligible for Cohort 3.

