7.7 Missed Injection Target Dose Timeline

Protocol Title: **CAB-RPV LA Implementation Strategies for High-Risk Populations**

In order to ensure that patients receive their injection within the 7 days of their target injection date, the following outline will be followed. This outline is applicable for any missed dose:

- **Day 1 Post Target:** The study team will outreach to the participant via their preferred communication method as specified in their locator form in order to encourage them to return within the following three days. The encounter will be tracked in the study Log Book.
- **Day 3 Post Target:** The study team will outreach again to the participant via the preferred communication method to encourage them to return the following day. The encounter will be tracked in the study Log Book.
- **Days 5-7 Post Target:** The study team will enlist BMC's ARCH and PT street-based outreach workers who are experienced with and successful at reaching and engaging high-risk patients. The outreach workers will conduct active outreach to the participant in the community to bring them in for a visit. If active outreach is unsuccessful, the study team will also use the contacts on the locator form to attempt to reach the participant. The encounter will be tracked in the study Log Book.
- **Upon Return Within 14 Days Post Target:** The study clinician will obtain a viral load and genotype. If the participant's viral load is less than 200 copies per mL, they will administer the CAB-RPV LA. If the participant's viral load is over 200 copies per mL, the study clinician will refer them to their primary care provider who will make the determination about whether or not an injection is appropriate. The encounter will be tracked in the study Log Book.
- **If participant returns after 15 days Post Target:**
 - **Missed Dose Occurs within 2 months of Initiation Injection:** The participant will be given a maintenance dose at their next contact with study staff (400mg/600mg 2 ml). The participant will then resume their normally scheduled injection plan, i.e. next injection scheduled to be given 25-32 days after maintenance dose administered.
 - **Missed Dose Occurs after first 2 months of injection:** The participant will be given a loading dose instead of their scheduled dosing amount (600mg/900 mg 3 ml). The participant will then resume their normally scheduled injection plan.

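### Section 7.1 reverses the viral-load limit for the first injection in Cohort 1 participants who skip the oral lead-in: it prints > 50 where < 50 copies/mL is meant

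*Combined protocol and SAP*

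**What the plan says.** Section 7.1, under the Cohort 1 study intervention, describes two routes to the first injection: an optional oral lead-in of up to 28 days, or none. For the second route it says: "If the participant chose's to not take the oral lead-in mediation, the participant will proceed directly to the initiation injection", on condition that all required lab work is complete, "including HIV labs confirming that they are virally suppressed (> 50 copies per mL"), together with a metabolic panel.

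The plan sets out the suppression requirement in several other places:

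- Section 5.1, Cohort 1 inclusion: "virally suppressed, meaning that their HIV-1 ribonucleic acid is less than 50 copies per mL".
- Section 5.2: "Individuals who are not virally suppressed prior to beginning CAB will be excluded", with Cohort 3 exempt.
- Section 7.1, screening: "Participants must be virally suppressed prior to enrollment, meaning that their HIV-1 ribonucleic acid measures less than 50 copies per mL".
- Section 7.1, on people found ineligible because they are unsuppressed: staff encourage them to re-engage in care and "reach out to study staff once their viral load is undetectable for enrollment".

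One other step makes an injection depend on a numeric viral load. Section 7.7 covers a participant who returns within 14 days after a missed target date: if the "viral load is less than 200 copies per mL, they will administer the CAB-RPV LA". Above 200, the participant is referred to the primary care provider, who decides.

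**The concern.** The sentence calls a participant suppressed and, in the same breath, gives a lower limit on viral load as the meaning of that word. Everywhere else in the plan suppression is an upper limit. Nor is this background text: it is the release condition for a first dose, and the only place in the no-lead-in procedure that states the numeric limit.

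Followed to the letter, the condition would hold back every properly enrolled participant on this route whose viral load was still below 50. It would release the first long-acting injection to someone whose viral load had risen above 50. Section 4.1 names resistance to cabotegravir and rilpivirine as a risk of non-adherence to the injections, so the viral-load condition for a first dose should not be left ambiguous.

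**Working it through.** No statistical calculation applies. The question is the direction of one inequality, so the check sets the rules side by side.

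**Inputs**

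- Rule A, eligibility (Section 5.1 and Section 7.1 screening): suppressed if viral load < 50 copies/mL.
- Rule B, first injection without lead-in, as printed (Section 7.1, Cohort 1 study intervention): suppressed if viral load > 50 copies/mL.
- Rule C, Rule B with the sign corrected: suppressed if viral load < 50 copies/mL.

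**Step 1: can A and B both be met?** A needs a value below 50 and B a value above 50. No value meets both, and exactly 50 meets neither. The two statements cannot be reconciled by interpretation.

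**Step 2: example values.** The three viral loads are chosen only for illustration.

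| Viral load (copies/mL) | Rule A: eligible | Rule B: first injection, as printed | Rule C: first injection, corrected |
|---|---|---|---|
| 20 | yes | no | yes |
| 100 | no | yes | no |
| 500 | no | yes | no |

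Rule B disagrees with Rule A at all three values. Rule C agrees at all three.

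**Step 3: which direction was intended?** Four things in the plan point the same way.

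- Two separate statements, in Sections 5.1 and 7.1, give the limit in words as below 50.
- Section 5.2 bars unsuppressed people before they begin the drug, which covers the first injection as well as enrollment.
- The Section 7.1 advice to people turned away makes an undetectable viral load the condition for coming back.
- Section 7.7 also uses an upper limit to release an injection. Its figure of 200 applies to return after a missed dose, so it supports the direction of the limit but not the value 50. It neither competes with the definition of suppression nor explains the printed sign.

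**Step 4: who is affected?** Only Cohort 1 participants who skip the lead-in. The lead-in procedure prints no such threshold. Cohorts 2 and 3 receive no study intervention beyond data collection (Section 6.0).

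**The case against.** The strongest reply is that nobody would be misled. The operative word is suppressed, which the plan defines correctly elsewhere. A participant who reaches this step has already been screened below 50, study clinicians review the records and decide eligibility, and Section 7.1 requires all activities to be on label. A trained HIV clinician would see a typing error, and the same sentence contains other slips. This stands as a limit on consequence and is why the point is minor. It does not make the sentence correct. Section 7.1 also says the initiation injection cannot be given on the day of enrollment, so the dosing step is separate from the enrollment visit, and staff working from the procedure should not have to check it against Section 5.1.

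A second reply is that the sign may have been misread when the PDF was converted to text. That cannot be fully excluded. However, nothing around the phrase is broken or blacked out, and inequality signs elsewhere came through in the sensible direction, such as the age limit in Section 5.1 and the 10% and 0.2 cut-offs in Section 11.3. If the sponsor's own copy shows <, the point closes at once.

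A third reply is that Section 7.7 is a weak comparison because it concerns a different situation and, above 200, refers the participant rather than refusing the injection. That is fair. The contradiction rests on Sections 5.1 and 7.1 alone.

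**Conclusion.** The concern holds: the threshold is wrong as written. The printed condition and the eligibility rule have no viral load in common, and the rest of the plan leaves no doubt that below 50 was meant. Severity is minor. The other statements of the rule and clinician review make it unlikely that anyone would be dosed or held back wrongly because of it. It does not affect the sample size, H1 or any other hypothesis in Section 11. The conclusion assumes that the text as read matches the sponsor's document at this character.

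**What to change.** In Section 7.1, Cohort 1 study intervention, in the sentence on participants who do not take the oral lead-in, replace > 50 copies per mL with < 50 copies per mL. No other edit is needed.

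The change is one character. It adds no test, visit or analysis and leaves eligibility under Sections 5.1 and 5.2 as it is. Section 13 sends amendments to the IRB, so the only real cost is that submission, and the correction could be included with the next amendment.
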